1127 7.3. OTHER OUTCOME MEASURES

1128 In addition to the primary and secondary outcome measures defined above, distribution of data 1129 and summary statistics will be evaluated on the following at each time point where relevant data 1130 are collected: IOP, impression cytology, corneal opacification, visual acuity, AS-OCT outcomes 1131 (central corneal epithelial thickness and limbal epithelial thickness in superior, inferior, nasal, 1132 and temporal quadrants), and IVCM outcomes (presence of corneal epithelial cells, presence of 1133 conjunctival epithelial cells, and the presence of limbal palisades of Vogt.) All reported adverse 1134 events will also be tabulated.

1135

1104

1105

1106 1107

1108

1109

1110

1111

1112 1113

1114

1115

1116

1117

1118

1119

1136 8. MONITORING STUDY PROGRESS

- 1137 Study progress will be monitored weekly or bi-weekly on Operations Committee calls.
- 1138 Recruitment reports will be available on the study website to monitor recruitment progress and
- 1139 ultimately follow up completion relative to the projected timeline. Operations Committee calls will
- also serve to keep all units of the Coordinating Center, Clinical Center, and PIs informed and
- 1141 engaged with the day-to-day progress of whether study goals are being met, including
- successful study oversight (including safety monitoring and protocol adherence monitoring of
- the monitoring plan) and eventually plans for closeout, manuscripts, and dissemination of study
- results. The Operations Committee will also monitor study progress with regards to timeliness
- 1145 and achievement of study goals.
- 1146

1148

1157

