- Inability to tolerate monitored anesthesia
- Current pregnancy (positive urine test) or lactation, or intent to become pregnant between enrollment and the first 3 months after transplant
- Participation in another simultaneous medical investigation or trial
- Any medical, psychiatric, debilitating disease/disorder or social condition that in the
 judgment of the investigator would interfere with or serve as a contraindication to adherence
 to the study protocol or ability to give informed consent
- Signs of current infection, including fever and current treatment with antibiotics
- Presence of potential allergy to the CALEC graft or any of the chemical components within
 its formulation
- 232

233 **5.2.2. EXCLUSION BASED ON EITHER EYE**

- Prior corneal surgery within 30 days prior to study entry except placement of amniotic
 membrane
- Corneal or ocular surface infection within 30 days prior to study entry or CALEC type
 transplantation
- Ocular surface malignancy
- Severe cicatricial eye disease
- 240 241

242

243

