- 383 Study participants who are determined to be ineligible for any reason (including 0 384 pregnancy) prior to biopsy will not proceed to biopsy or transplant, and will either 385 discontinue or postpone and re-screen at a later time. 386 After biopsy but prior to transplant 387 Study participants who become pregnant will consult with the study doctor and their \circ 388 Obstetrician/Gynecologist or primary care physician before determining if it is safe for 389 them to continue with the transplant procedure. If the decision is made not to 390 continue with the transplant procedure, the participant will either discontinue or 391 postpone and re-screen at a later time. 392 Study participants who are determined to be ineligible for any other reason will 0 393 consult with the study doctor before determining if it is safe for them to continue with 394 the transplant procedure. If the decision is made not to continue with the transplant 395 procedure, the participant will either discontinue or postpone and re-screen at a later 396 time. 397 Study participants for whom the biopsy fails to generate a viable cell sheet may be 0 398 evaluated for a second biopsy according to Section 5.6 above. If the participant does 399 not proceed to second biopsy for any reason, or a second biopsy also fails to 400 generate a viable cell sheet, the participant will discontinue. 401 Additionally: Regardless of whether a participant will discontinue, all participants 0 402 who had a biopsy and do not proceed to transplant will be monitored by the study team for 30 days to check for any adverse events related to the biopsy procedures. 403 404 If the donor eye after biopsy has a complication or adverse event that does not 405 resolve after 30 days, the study team will also monitor the donor eye until the 406 complication resolves. Those meeting criteria to discontinue, as detailed in the 407 scenarios above, will discontinue after this time. 408 After transplant 409 In general, all possible efforts will be employed to ensure participants who completed 0
- 410
- In general, all possible efforts will be employed to ensure participants who completed transplant are retained through the duration of follow up.

411412 **5.8. TERMINATION OF STUDY**

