769 the procedure and a temporary bandage contact lens may be applied prior to imaging for patient 770 comfort and removed after imaging. One drop of hypromellose 2.5% is applied to the patient's eye and one drop of hypromellose 0.3% will be placed on the objective lens of the microscope 771 772 according to the manufacturer's instructions. IVCM will be performed on each eye with a 773 Heidleberg retina tomograph (HRTII)/Rostock cornea module (RCM) (Heidelberg Engineering 774 GmbH, Dossenheim, Germany) with a water-immersion objective lens. One scan of the central 775 cornea and one scan of each quadrant of the limbus (superior, nasal, temporal, and inferior) will 776 be obtained. IVCM of both eyes will be performed at the baseline visit, 12 and 18-month post-777 operative visits unless patient reports eye pain, discomfort, irritation and cannot tolerate the 778 procedure, or there is clinical contraindication in the case of corneal epithelial defect, 779 hemorrhage, or inflammation. Images will be analyzed to determine the presence or absence of 780 the following cell types: corneal epithelial cells are defined as polygonal cells with bright, well-781 defined borders, dark cytoplasm and no visible nuclei; conjunctival cells are defined as cells with 782 bright nuclei and ill-defined borders. Limbal palisades of Vogt are defined as hyper-reflective 783 double contoured linear structures that alternate with islands of epithelial cells. The outcomes 784 are: presence (or absence) of corneal epithelial cells in the central cornea and limbus, presence 785 (or absence) of conjunctival epithelial cells in the central cornea and limbus, and the presence 786 (or absence) of limbal palisades of Vogt. There may be future analysis of the images that are 787 currently unknown. IVCM will be done by a certified study photographer or research associate. 788 789 **6.7. LABORATORY EVALUATIONS** 790 Participants will have blood drawn at the Massachusetts Eye and Ear Infirmary Clinical

Participants will have blood drawn at the Massachusetts Eye and Ear Infirmary Clinical Laboratory at screening (see list of tests run at screening). An additional blood draw will be collected within 7 days before or after biopsy to test for Hepatitis B, Hepatitis C, and HIV, and results communicated to CMCF prior to release of the product.

794

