Additionally, female participants of child-bearing potential will undergo a urine pregnancy test at screening for study eligibility determination and then again at the visit before CALEC

- 797 transplantation.
- 798

Participants with uncontrolled diabetes, as defined by the most recent HbA1c >8.5% (at the screening visit or within 3 months prior to screening visit) and with decreased renal function, as

- 801 defined by eGFR (estimated glomerular filtration rate) below 60 mL/min per 1.73 m², will be 802 excluded from the study. Similarly, we will check lab values for liver enzymes, hemoglobin,
- 802 excluded from the study. Similarly, we will check lab values for liver enzymes, hemoglobin, 803 platelets, prothrombin time, partial thromboplastin time, and international normalized ratio.
- Aspartate aminotransferase or alanine aminotransferase levels >3x institutional upper limit of
- normal will be considered abnormal. Total bilirubin >2.0x institutional upper limit of normal
- 806 (except participants with known Gilbert's syndrome) will be considered abnormal. Further,
- platelet levels <100,000 or >450,000 per microliter, and male hemoglobin of <11.0 g/dL, and
- 808 female hemoglobin levels of <10.0 g/dL, will also be consider abnormal. Finally, prothrombin
- time >16 seconds or activated partial thromboplastin time >35 seconds in participants not taking
- 810 warfarin, and an international normalized ratio >3 in participants taking warfarin, will be
- 811 considered abnormal. Participants testing positive for HIV or AIDS or active hepatitis B or C will
- 812 also be excluded. If any of these lab values are found to be abnormal, the participants will be
- 813 excluded and referred to their primary care physicians for further workup and treatment.
- 814

815 6.8. STUDY SCHEDULE

- 816 Below is a summary of the study visit schedule. The following sections summarize all
- assessments performed at each visit. The MOP provides more details regarding the order of
- 818 testing. For a summary table of study visit schedule and all assessments performed, see

819 Appendix VII. All visits occur after the participant has been enrolled (after obtaining informed 820 consent).

- 821
- 822 Screening Visit
- **Baseline Visit** –required within 30 days of Screening Visit
- **Biopsy** required within 25 days of Baseline Visit
- **Post-Biopsy Visit** required 1 day after biopsy
- **Pre-operative Visit** required 1 to 5 days prior to transplant

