864 865 866 867 868 869 870 871 872 873 874 874 875	 eGFR HbA1c, if needed (does not need to be repeated at screening visit if done within the last 3 months prior to screening visit) Aspartate aminotransferase and alanine aminotransferase levels Bilirubin levels Prothrombin and thromboplastin time Urine pregnancy test for women of childbearing potential Slit lamp examination (both eyes), including Corneal opacification (as defined by Fantes Scale) (both eyes) Staining with fluorescein (extent of staining and epithelial defect area) (both eyes) Visual Acuity BCVA (both eyes)
876	Conjunctival swab and culture (both eyes)
877	Intraocular pressure (both eyes)
878	 Fundus examination or B-scan ultrasound (both eyes)
879	Slit lamp photographs (both eyes) by certified technician, including
880	 Photography for neovascular area
881	 Photography (with fluorescein) for epithelial defect
882	 Schirmer's test with anesthesia (both eyes)
883	Referral to primary care physician to confirm general health prior to surgery, as needed
884	according to MEEI hospital SOPs
885	 Punctal plugs, if needed (Section 6.5.5) (both eyes)
887 888 889 890 891 892 893	In addition, blood draw will be performed for autologous serum eye drops prior to transplantation per CMCF guidelines. 6.8.2. BASELINE (WITHIN 30 DAYS OF SCREENING VISIT) A baseline visit will be conducted after a participant is considered eligible to participate as determined by the screening visit. Baseline visit procedures must occur within 30 days after the screening visit
894	
895	Baseline procedures may be conducted over multiple visits after screening.
896	
897	The following procedures will be conducted for the baseline visit:
898 899 900	Review of pre-operative health screening results to confirm general health prior to surgery according to MEEL bospital SOPs
900	Slit lamp examination (both eves) including
902	 Corneal opacification (as defined by Fantes Scale) (both eves)
903	 Staining with fluorescein (extent of staining and epithelial defect area) (both eves)
904	 Visual acuity BCVA (both eves)
905	 Intraocular pressure (both eves)
906	Slit lamp photographs (both eyes) by certified technician, including
907	\circ Photography for neovascular area
908	 Photography (with fluorescein) for epithelial defect
909	Anterior Segment Optical Coherence Tomography
910	In Vivo Confocal Microscopy
911	 Punctal plugs, if needed (Section 6.5.5) (recipient eye only)
912	 Assessment of changes in medical conditions since screening

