913	Symptom assessment

- 914
- 915

918

916 In addition, within seven days before or after limbal biopsy, blood draw will be performed for 917 donor serology testing in CALEC participants only.

919 6.8.3. LIMBAL BIOPSY (WITHIN 25 DAYS OF BASELINE VISIT)

920 Following the baseline visit, a biopsy of the donor eye will be taken as an outpatient procedure 921 for all participants receiving the CALEC. The biopsy must occur within 25 days after the 922 baseline visit. Refer to section 6.2.

923

924 6.8.4. TRANSPORTATION OF TISSUE TO CMCF & PREPARATION OF CALEC

925 If participants are enrolled in the CALEC arm, the tissue taken from the donor eye during the 926 biopsy will be taken to Connell and O'Reilly Families Cell Manipulation Core Facility (CMCF) at 927 the Dana-Farber Cancer Institute (DFCI) per operating procedures (MOP, Section 7).

928

929 6.8.5. POST-BIOPSY ASSESSMENT OF DONOR EYE (1-2 DAYS AFTER CALEC BIOPSY)

- 930 Slit lamp examination (donor eye) including • 931
 - Staining with fluorescein (extent of staining and epithelial defect area)
- 932 • Visual acuity (BCVA) (donor eye)
- 933 • Intraocular pressure (donor eye)
- 934 Adverse event assessment
- 935 • Slit lamp photos (donor eve) by certified technician, including: 936 • Photography (with fluorescein) for epithelial defect
- 937 • Punctal plug placement, if needed (Section 6.5.5)

938 939 6.8.6. TRANSPORTATION OF CALEC FROM CMCF TO MEEI

940 The CALEC is anticipated to be released 10 to 30 days after biopsy, upon which it will be

- 941 transported from CMCF to MEEI (MOP, Sections 7.1.3 and 7.1.4).
- 942

943 6.8.7. PREOPERATIVE ASSESSMENT OF RECIPIENT EYE (1 TO 5 DAYS PRIOR TO 944 TRANSPLANT)

- 945 A preoperative assessment will be evaluated prior to reconstruction to confirm fitness for
- 946 reconstruction of the recipient eye. All participants will receive this preoperative assessment 1 to 947 5 days prior to the day of corneal reconstruction (transplant).
- 948

952

953

954

949 The following procedures will be performed at these visits:

- 950 • Urine pregnancy test for women of childbearing potential
- 951 Slit lamp examination (recipient eye) including •
 - Corneal opacification (as defined by Fantes Scale)
 - Staining with fluorescein (extent of staining and epithelial defect area)
 - Visual acuity BCVA (recipient eye)
- 955 • Intraocular pressure (recipient eye)
- 956 Adverse event assessment
- 957 • Punctal plugs, if needed (Section 6.5.5) (both eyes)
- 958

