959 Participants will be asked to report any pregnancies that occur within three days prior to 960 surgery. 961

962 6.8.8. CORNEAL RECONSTRUCTION WITH CALEC (DAY 0)

963 Participants will undergo corneal reconstruction within 24 hours of release of CALEC.

964	
965	A detailed description of the procedures can be found in Section 6.2.2. All participants will be
966	discharged the day of surgery, unless unforeseen complications prohibit discharge. If a
967	participant is admitted for observation, the Day 1 post-operative visit will occur while the
968	participant is in the hospital. All other visits will follow as originally scheduled.
969	
970	6.8.9. FOLLOW-UP PERIOD
971	Each participant will be followed for a period of 18 months from the time of the transplantation.
972	
973	Participants will be asked to report any pregnancies that occur within seven days after
974	transplant.
975	
976	6.8.10. POST-TRANSPLANT (DAY 1)
977	Slit lamp examination (both eyes) including
978	 Corneal opacification (as defined by Fantes Scale) (both eyes)
979	• Staining with fluorescein (extent of staining and epithelial defect area) (donor eye
980	required; recipient eye at discretion of investigator)
981	 Visual acuity (BCVA)(both eyes)
982	Intraocular pressure (both eyes)
983	Slit lamp photographs (both eyes) by certified technician, including
984	 Photography for neovascular area
985	• Photography (with fluorescein) for epithelial defect (donor eye required; recipient
986	eye at discretion of clinician)
987	 Punctal plugs, if needed (Section 6.5.5) (both eyes)
988	 Application of bandage contact lens, if needed (Section 6.5.5)
989	Adverse event assessment
990	
991	6.8.11. POST-OP FOLLOW-UP: WEEKS 1, 2, MONTH 1 (4 WEEKS ± 3 DAYS) AND
992	MONTHS 3, 6, 9, 12 (13, 26, 39, 52 WEEKS ± 1 WEEK), AND MONTHS 15, AND 18 (65 AND
993	78 WEEKS ±2 WEEKS)
994	 Symptom assessment (every visit except week 1, week 2, month 1)
995	 Slit lamp examination (both eyes) including
996	 Corneal opacification (as defined by Fantes Scale) (both eyes)
997	 Staining with fluorescein (extent of staining and epithelial defect area) (donor eye
998	required; recipient eye at discretion of investigator at week 1 and 2, and required at
999	month 1 and thereafter.)
1000	 Visual acuity BCVA (both eyes)
1001	Intraocular pressure (both eyes)
1002	 Slit lamp photographs (both eyes) by certified technician, including
1003	 Photography for neovascular area

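### No pregnancy test is scheduled between Screening and the donor-eye biopsy, so the last scheduled result can be up to 55 days old at biopsy (minor participant-protection point)

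*Protocol*

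**What the plan says.** Protocol section 5.2.1 excludes "Current pregnancy (positive urine test) or lactation", and the same criterion also excludes women who intend to conceive at any time from enrollment to 3 months after transplant. Section 5.7 keeps anyone found ineligible before the biopsy, pregnancy included, from going on to biopsy or transplant. It sets the consequence of a pregnancy but schedules no test.

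The tests are placed by section 6.7: women of childbearing potential "will undergo a urine pregnancy test at screening for study eligibility determination and then again at the visit before CALEC" transplantation. The Screening list (6.8.1) and the preoperative list (6.8.7) each carry the item "Urine pregnancy test for women of childbearing potential". The Appendix VI row marks Screening and Pre-Op only. The Baseline list (6.8.2), the biopsy section (6.8.3) and the post-biopsy list (6.8.5) have no such item. Baseline does include "Assessment of changes in medical conditions since screening".

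Before the transplant there is a further check. Section 6.8.7 adds: "Participants will be asked to report any pregnancies that occur within three days prior to" surgery. No matching request precedes the biopsy.

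**The concern.** Pregnancy is an exclusion, and section 5.7 treats it as a reason not to biopsy. After Screening, however, no scheduled test supports that rule until the biopsy has been done. A site that followed the schedule exactly could biopsy the healthy eye of a participant who is excluded, without anyone knowing.

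The pregnancy would then first be tested for at Pre-Op. At that stage section 5.7 calls for consultation with the study doctor and the participant's obstetrician/gynecologist or primary care physician, and the transplant may not go ahead. The participant would have had surgery on her good eye without the intended graft, and would have used one of the two biopsies that section 5.6 allows. What is at stake is participant protection, not any estimate.

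**Working it through.** **Inputs (protocol)**
- Screening to Baseline: at most 30 days (6.8, 6.8.2).
- Baseline to biopsy: at most 25 days (6.8). Section 6.8.3 repeats it: "The biopsy must occur within 25 days after the" Baseline visit.
- Biopsy to transplant: expected to be 10 to 30 days (6.8).
- Pre-Op visit: 1 to 5 days before transplant (6.8.7).
- Second biopsy: at least 30 days after the first. Screening is repeated unless the second biopsy falls within 55 days of the first Screening visit (5.6).

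**1. First biopsy.** Maximum age of the Screening test = 30 + 25 = 55 days. This reproduces the 55-day limit in section 5.6, so the windows have been read as the protocol intends.

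**2. Could the Pre-Op test come before the biopsy?** Earliest: 10 − 5 = 5 days after biopsy. Latest: 30 − 1 = 29 days after biopsy. On the expected timing it always follows the biopsy. Because section 6.8.8 places the transplant within 24 hours of product release, Pre-Op generally falls late in manufacture and before release.

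**3. Second biopsy under 5.6, only Baseline repeated.** The second biopsy is at least 30 days after the first, which cannot precede Screening, and at most 55 days after Screening. The Screening test is therefore 30 to 55 days old. This route is open only if the first biopsy took place by day 55 − 30 = 25 after Screening. If a Pre-Op visit had already been held before the first attempt failed, a more recent test would exist.

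**4. Second biopsy under 5.6, full rescreening.** Again at most 30 + 25 = 55 days.

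**5. With a test added.** On the day of biopsy: 0 days. At Baseline: at most 25 days.

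**6. Second CALEC (section 15.4).** The section starts from the 6.8.1–6.8.2 procedures, which include the urine test, and then lists exceptions. Its laboratory exception concerns hematologic screening, and Appendix VI shows the pregnancy test as a separate row from hematologic screening. The better reading is that the test carries over. However, the list of contents for the combined visit does not name it, and the section also says that the full set of labs is not repeated.

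**The case against.** The case for leaving the schedule alone has real content.

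- **Other safeguards exist.** The exclusion for intended pregnancy covers the whole interval from Screening to biopsy, and the Baseline review should bring out a known pregnancy. This stands. It narrows the gap to a pregnancy that is both unintended and unrecognised, but it does not close it.
- **Sources not seen may close it.** Section 6.2.2.1 relies on standard operating procedures at the surgery center, Baseline reviews pre-operative health results under hospital procedures, and the MOP holds further detail. A reader might infer that no test is done before biopsy. The documents show only that the protocol names none.
- **The 55-day validity looks deliberate.** Section 5.6 uses the same limit for repeating Screening. That makes this a design choice and not an inconsistency. Even so, the protocol does not let the Screening result stand until transplant: it retests 1 to 5 days beforehand.
- **The harm is not spelled out.** The documents name no fetal hazard from the biopsy and no way in which pregnancy raises the risk to the donor eye. After biopsy, section 5.7 does not make pregnancy an absolute bar even to transplant. This stands, and it keeps the point minor. The argument rests on enforcing the protocol's own exclusion, not on a demonstrated injury.

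A reader might also cite the serology draw in section 6.7 as a pre-biopsy check from which pregnancy was left out. The documents do not support that. The wording is "An additional blood draw will be collected within 7 days before or after biopsy", and the results go to the manufacturing facility before product release, so the draw is not a safety check before biopsy.

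**Conclusion.** The point holds as a minor improvement in participant protection. For a first biopsy, or a second biopsy after full rescreening, the last scheduled pregnancy test can be up to 55 days old. For a second biopsy with only Baseline repeated, it is 30 to 55 days old unless a Pre-Op visit was already held. These are limits set by the visit windows; the documents do not give the typical interval.

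Three stronger readings should be resisted. Participants are not unprotected between Screening and biopsy, because the intent exclusion and the Baseline review both apply. The addendum does not clearly drop the test for a second CALEC; it more likely carries over without being named. And no safety, feasibility or efficacy estimate is affected.

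The number of women of childbearing potential is not given. With a target of 17 transplants, few participants can be involved. The conclusion assumes that the protocol's schedule is what the site follows and that no document outside it already requires a test before biopsy.

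**What to change.** Add a urine pregnancy test for women of childbearing potential before every biopsy, preferably on the day of biopsy and otherwise at Baseline. Enter it in section 6.7, in 6.8.2 or 6.8.3, and in Appendix VI, worded so that it also covers second biopsies under 5.6. Keep the Pre-Op test. Handle a positive result as section 5.7 already states. Name the test in the section 15.4 visit list for a second CALEC. If hospital procedures or the MOP already require a test before biopsy, say so in the protocol, as is done for the transplant.

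The cost is one extra urine test per biopsy: at most 2 per woman under the two-biopsy limit in 5.6, plus 1 for a second CALEC, so at most 2 + 1 = 3. A biopsy will occasionally be postponed. A positive result on the day loses an operating slot. Testing at Baseline avoids most of that loss but leaves up to 25 days uncovered.
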